10.2 Section 14 Summary Tables and Figures

The following is a list of table and figure titles that will be included in Section 14 of the report. Table and figure titles may be renumbered as appropriate during the compilation of the report.

14.1 Demographic Data Summary Tables

Table 14.1.1 Summary of Disposition (Safety Population)

Table 14.1.2 Demographic Summary (Safety Population)

14.2 Pharmacokinetic/Pharmacodynamic Data Summary Tables and Figures

14.2.1 Plasma S 48168 (ARM210) Tables

Table 14.2.1.1 Plasma S 48168 (ARM210) Concentrations (<units>) Following Single Oral Administration of 120 mg S 48168 (ARM210) (6 x 20 mg Tablets) for 28 Days (Patients) (Treatment A) (Days 1-28) (Pharmacokinetic Population)

Table 14.2.1.2 Plasma S 48168 (ARM210) Concentrations (<units>) Following Single Oral 200 mg S 48168 (ARM210) (10 x 20 mg Tablets) for 28 Days (Patients) (Treatment B) (Days 1-28) (Pharmacokinetic Population)

Table 14.2.1.3 Plasma S 48168 (ARM210) Concentrations (<units>) Following Single Oral 120 mg S 48168 (ARM210) (3 x 40 mg Tablets) for 14 Days (Healthy Subjects) (Treatment C) (Days 1-14) (Pharmacokinetic Population)

Table 14.2.1.4 Plasma S 48168 (ARM210) Concentrations (<units>) Following Single Oral 240 mg S 48168 (ARM210) (1 x 200

mg and 1 x 40 mg Tablets) for 14 Days (Healthy Subjects) (Treatment D) (Days 1 - 14) (Pharmacokinetic Population)

Table 14.2.1.5 Plasma S 48168 (ARM210) Pharmacokinetic Parameters Following Single Oral Administration of 120 mg S 48168 (ARM210) (6 x 20 mg Tablets) for 28 Days (Patients) (Treatment A) (Day 1) (Pharmacokinetic Population)

Table 14.2.1.6 Plasma S 48168 (ARM210) Pharmacokinetic Parameters Following Single Oral Administration of 120 mg S 48168 (ARM210) (6 x 20 mg Tablets) for 28 Days (Patients) (Treatment A) (Day 28) (Pharmacokinetic Population)

Table 14.2.1.7 Plasma S 48168 (ARM210) Pharmacokinetic Parameters Following Single Oral 200 mg S 48168 (ARM210) (10 x 20 mg Tablets) for 28 Days (Patients) (Treatment B) (Day 1) (Pharmacokinetic Population)

Table 14.2.1.8 Plasma S 48168 (ARM210) Pharmacokinetic Parameters Following Single Oral 200 mg S 48168 (ARM210) (10 x 20 mg Tablets) for 28 Days (Patients) (Treatment B) (Day 28) (Pharmacokinetic Population)

Table 14.2.1.9 Plasma S 48168 (ARM210) Pharmacokinetic Parameters Following Single Oral 120 mg S 48168 (ARM210) (3 x 40 mg Tablets) for 14 Days (Healthy Subjects) (Treatment C) (Day 1) (Pharmacokinetic Population)

Table 14.2.1.10 Plasma S 48168 (ARM210) Pharmacokinetic Parameters Following Single Oral 120 mg S 48168 (ARM210) (3 x 40 mg Tablets) for 14 Days (Healthy Subjects) (Treatment C) (Day 14) (Pharmacokinetic Population)

Table 14.2.1.11 Plasma S 48168 (ARM210) Pharmacokinetic Parameters Following Single Oral 240 mg S 48168 (ARM210) (1 x 200 mg and 1 x 40 mg Tablets) for 14 Days (Healthy Subjects) (Treatment D) (Day 1) (Pharmacokinetic Population)

Table 14.2.1.12 Plasma S 48168 (ARM210) Pharmacokinetic Parameters Following Single Oral 240 mg S 48168 (ARM210) (1 x 200 mg and 1 x 40 mg Tablets) for 14 Days (Healthy Subjects) (Treatment D) (Day 14) (Pharmacokinetic Population)

Table 14.2.1.12 Intervals (Hours) Used for Determination of Plasma S 48168 (ARM210) Kel Values (Pharmacokinetic Population)

14.2.2 Plasma S 48168 (ARM210) Figures

Figure 14.2.2.1 Mean (SD) Plasma S 48168 (ARM210) Concentration-Time Profiles of Following Single Dose Administration of 120 mg, 200 mg, and 240 mg S 48168 (ARM210) on Day 1 (Treatments A, B, C, and D) (Linear Scale) (Pharmacokinetic Population)

Figure 14.2.2.2 Mean Plasma S 48168 (ARM210) Concentration-Time Profiles of Following Single Dose Administration of 120 mg, 200 mg, and 240 mg S 48168 (ARM210) on Day 1 (Treatments A, B, C, and D) (Linear Scale)

Figure 14.2.2.3 Mean Plasma S 48168 (ARM210) Concentration-Time Profiles of Following Single Dose Administration of 120 mg, 200 mg, and 240 mg S 48168 (ARM210) on Day 1 (Treatments A, B, C, and D) (Semi-Log Scale)

Figure 14.2.2.4 Mean (SD) Plasma S 48168 (ARM210) Concentration-Time Profiles of Following Multiple Daily Doses 120 mg and 200 mg S 48168 (ARM210) in Patients (Day 28) and 120 mg and 240 mg S 48168 (ARM210) in Healthy Subjects (Day 14) (Linear Scale) (Pharmacokinetic Population)

Figure 14.2.2.5 Mean Plasma S 48168 (ARM210) Concentration-Time Profiles of Following Multiple Daily Doses 120 mg and 200 mg S 48168 (ARM210) in Patients (Day 28) and 120 mg and 240 mg S 48168 (ARM210) in Healthy Subjects (Day 14) (Linear Scale)

Figure 14.2.2.6 Mean Plasma S 48168 (ARM210) Concentration-Time Profiles of Following Multiple Daily Doses 120 mg and 200 mg S 48168 (ARM210) in Patients (Day 28) and 120 mg and 240 mg S 48168 (ARM210) in Healthy Subjects (Day 14) (Semi-Log Scale)

Note to Programmer: For Figures 14.2.2.4 through 14.2.2.6 superimpose both the Days 14 and 28 for All figures are to be generated in color.

14.2.3 Pharmacodynamic/Target Engagement Tables

Table 14.2.3.1 Mean % RyR1-Calstabin1 Binding

14.2.4 Motor Function and Quality of Life Tables

Table 14.2.4.1 Summary of Timed Functional Tests

Table 14.2.4.2 Summary of Motor Function Measure 32

Table 14.2.4.3 Summary of Quality of Life Questionnaire

14.3 Safety Data Summary Tables

14.3.1 Displays of Adverse Events

Table 14.3.1.1 Treatment-emergent Adverse Event Frequency by Treatment – Number of Subjects Reporting the Event (% of Subject Dosed) (Safety Population)

Table 14.3.1.2 Treatment-emergent Adverse Event Frequency by Treatment – Number of Adverse Events (% of Total Adverse Events) (Safety Population)

Table 14.3.1.3 Treatment-emergent Adverse Event Frequency by Treatment, Severity, and Relationship to Drug – Number of Adverse Events (Safety Population)

Table 14.3.1.4 Frequency of Treatment-emergent Adverse Event with Grade 2 or Greater Severity, are Serious, or Are of Special Interest by Treatment (Safety Population)

14.3.2 Listings of Deaths, other Serious and Significant Adverse Events

Table 14.3.2.1 Serious Adverse Events (Safety Population)
<if no serious adverse event occurred, a statement 'No serious adverse event is reported'>

14.3.3 Narratives of Deaths, other Serious and Certain other Significant Adverse Events

14.3.4 Abnormal Laboratory Value Listing (each patient)

Table 14.3.4.1 Out-of-Range Values and Recheck Results – Serum Chemistry (Safety Population)

Table 14.3.4.2 Out-of-Range Values and Recheck Results – Hematology (Safety Population)

Table 14.3.4.3 Out-of-Range Values and Recheck Results – Urinalysis (Safety Population)

14.3.5 Displays of Other Laboratory, Vital Signs, Electrocardiogram, Physical Examination, and Other Safety Data

Table 14.3.5.1 Clinical Laboratory Summary and Change from Baseline – Serum Chemistry (Safety Population)

Table 14.3.5.2 Clinical Laboratory Shift from Baseline – Serum Chemistry (Safety Population)

Table 14.3.5.3 Clinical Laboratory Summary and Change from Baseline – Hematology (Safety Population)

- Table 14.3.5.4 Clinical Laboratory Shift from Baseline – Hematology (Safety Population)
- Table 14.3.5.5 Clinical Laboratory Summary and Change from Baseline – Urinalysis (Safety Population)
- Table 14.3.5.6 Clinical Laboratory Shift from Baseline – Urinalysis (Safety Population)
- Table 14.3.5.7 Vital Sign Summary and Change from Baseline (Safety Population)
- Table 14.3.5.8 12-Lead Electrocardiogram Summary (Safety Population)

14.4 Section 16 Data Listings

Data listings are numbered following the ICH structure but may be renumbered as appropriate during the compilation of the TFLs for the CSR. The following is a list of appendix numbers and titles that will be included as data listings:

16.1 Study Information

Appendix 16.1.9 Statistical Methods

Appendix 16.1.10.1 Clinical Laboratory Reference Ranges

16.2 Subject Data Listings

16.2.1 Subject Discontinuation

Appendix 16.2.1 Subject Discontinuation (Safety Population)

16.2.2 Protocol Deviations

Appendix 16.2.2 Protocol Deviations

16.2.3 Subjects Excluded from Pharmacokinetic Analysis

Appendix 16.2.3 Subjects Excluded from Pharmacokinetic Analysis

Note: Appendices 16.2.2 and 16.2.3 are generated in MS Word for inclusion in the study report.

16.2.4 Demographic Data

Appendix 16.2.4.1 Subject Information (Safety Population)

Appendix 16.2.4.2 Demographics (Safety Population)

Appendix 16.2.4.3 Physical Examination - Full (Safety Population)

Appendix 16.2.4.4 Physical Examination – Symptom Driven (Safety Population)

Appendix 16.2.4.5 Medical and Surgical History (Safety Population)

Appendix 16.2.4.6 Tobacco Use (Safety Population)

Appendix 16.2.4.7 CYP2C8 Genotyping (Safety Population)

Appendix 16.2.4.8 Echocardiogram (Safety Population)

Appendix 16.2.4.9 Pulmonary Function Test (Safety Population)

16.2.5 Compliance and/or Drug Concentration Data

Appendix 16.2.5.1 Inclusion/Exclusion Criteria not Met (Safety Population)

Appendix 16.2.5.2 Dose Administration Times (Safety Population)

Appendix 16.2.5.3 Pharmacokinetic Blood Sampling (Safety Population)

Appendix 16.2.5.4 Skeletal Muscle Needle Biopsy (Safety Population)

Appendix 16.2.5.5 Concomitant Medications (Safety Population)

Appendix 16.2.5.6 Subject Contact (Safety Population)

Appendix 16.2.5.7 Subject Diary (Safety Population)

16.2.6 Individual Pharmacokinetic/Pharmacodynamic Response Data

Appendix 16.2.6.1 Plasma S 48168 (ARM210) Concentrations Versus Time (Linear and Semi-Log Scale) for Subject #

Appendix 16.2.6.2 Percent (%) RyR1-Calstabin1 Binding (Pharmacodynamic Population)

Appendix 16.2.6.3 Motor Function Measure 32 (Safety Population)

Appendix 16.2.6.4 Graded Functional Testing (Safety Population)

Appendix 16.2.6.5 Grip and Pinch Strength (Safety Population)

Appendix 16.2.6.6 Fatigue Questionnaire (Safety Population)

Appendix 16.2.6.7 C-SSRS – Baseline – Suicidal Ideation (Safety Population)

Appendix 16.2.6.8 C-SSRS – Baseline – Intensity of Ideation (Safety Population)

Appendix 16.2.6.9 C-SSRS – Baseline – Suicidal Behavior (Safety Population)

Appendix 16.2.6.10 C-SSRS – Baseline – Actual Attempts (Safety Population)

Appendix 16.2.6.11 C-SSRS – Since Last Visit – Suicidal Ideation (Safety Population)

Appendix 16.2.6.12 C-SSRS – Since Last Visit – Intensity of Ideation (Safety Population)

Appendix 16.2.6.13 C-SSRS – Since Last Visit – Suicidal Behavior (Safety Population)

Appendix 16.2.6.14 C-SSRS – Since Last Visit – Actual Attempts (Safety Population)

16.2.7 Adverse Events Listings

Appendix 16.2.7.1 Adverse Events (I of II) (Safety Population)

Appendix 16.2.7.2 Adverse Events (II of II) (Safety Population)

Appendix 16.2.7.3 Adverse Event Preferred Term Classification (Safety Population)

16.2.8 Listings of Individual Laboratory Measurements and Other Safety Observations

Appendix 16.2.8.1.1 Clinical Laboratory Report - Serum Chemistry (Safety Population)

Appendix 16.2.8.1.2 Clinical Laboratory Report - Hematology (Safety Population)

Appendix 16.2.8.1.3 Clinical Laboratory Report - Urinalysis (Safety Population)

Appendix 16.2.8.1.4 Clinical Laboratory Report - Urine Drug Screening (Safety Population)

Appendix 16.2.8.1.5 Serology (Safety Population)

Appendix 16.2.8.1.6 Pregnancy Test (Safety Population)

Appendix 16.2.8.1.7 Serum FSH (Safety Population)

Appendix 16.2.8.1.8 Urine Alcohol Test (Safety Population)

Appendix 16.2.8.2 Vital Signs (Safety Population)

Appendix 16.2.8.3 12-Lead Electrocardiogram (Safety Population)

11. TABLE AND FIGURE SHELLS

The following table shells provide a framework for the display of data from this study. The shells may change due to unforeseen circumstances. These shells may not be reflective of every aspect of this study, but are intended to show the general layout of the tables that will be presented and included in the final report. Unless otherwise noted, all tables will be presented in Times New Roman font size 8. These tables will be generated off of the Celerion ADaM data structure. ADaM datasets are created in accordance with CDISC guidance (ADaM Model 2.1 and ADaM implementation guide 1.1).

Safety table shells will be completed at a later date.

11.1 In-text Summary Tables Shells

In-text Tables 11-2 and 11-3 will be in the following format:

Table 11-2 Summary of Plasma S 48168 (ARM210) Pharmacokinetics Following Single Dose of 120 mg, 200 mg, and 240 mg S 48168 (ARM210) (Treatments A, B, C, and D) (Day 1)

Pharmacokinetic Parameters	Treatment <Y>	Treatment <X>
Param1 (units)	XXX.X (XX.X) [n=xx]	XXX.X (XX.X) [n=xx]
Param2 (units)	XXX.X (XX.X) [n=xx]	XXX.X (XX.X) [n=xx]
Param3 (units)	XXX.X (XX.X) [n=xx]	XXX.X (XX.X) [n=xx]
Param4 (units)	XXX.X (XX.X) [n=xx]	XXX.X (XX.X) [n=xx]

Treatment <Y>: <Label for Second Treatment>
Treatment <X>: <Label for First Treatment>
AUCs and Cmax values are presented as geometric mean and geometric CV%.
Tmax values are presented as median (min, max).
Other parameters are presented as arithmetic mean (\pm SD).
Source: Tables <XXXX> and <YYYY>

Notes for Generating the Actual Table:

Treatments

Treatment A: Single oral 120 mg S 48168 (ARM210) QD for 28 days (patients)
Treatment B: Single oral 200 mg S 48168 (ARM210) QD for 28 days (patients)
Treatment C: Single oral 120 mg S 48168 (ARM210) QD for 14 days (healthy subjects)
Treatment D: Single oral 240 mg S 48168 (ARM210) QD for 14 days (healthy subjects)

Presentation of Data:

- The following PK parameters will be presented in the following order and with following units: Day 1: AUC0-t <unit>, AUC0-inf <unit>, AUC%extrap <unit>, Cmax <unit>, Tmax <unit>, Kel <unit>, t½ <unit>, and Tlag <unit>
Day 28: AUC0-tau <unit>, Cmax,ss <unit>, Tmax,ss <unit>, Cmin <unit>, Tmin <unit>, RA(AUC) <unit>, RA(Cmax) <unit>, and Cthrough_D13 <unit>
- n will be presented as an integer (with no decimal);
- Summary statistics will be presented with same precision as defined in post-text shells
- Table 11-2 source table is Tables 14.2.1.5, 14.2.1.7, 14.2.1.9, and 14.2.1.11.
- Table 11-3 source table is Tables 14.2.1.6, 14.2.1.8, 14.2.1.10, and 14.2.1.12.

Celerion Note: Per study design needs, the following changes are made to this table relative to Celerion's standard shell. For Tables 11-2 and 11-3 there will be a column for each Treatment. Put the "Treatment" as well as the "Dose Level" administered. Also add the Day in brackets.

Program: /CAXXXX/sas_prg/pksas/intext-pk-tables.sas DDMMYYYY HH:MM
Program: /CAXXXX/sas_prg/pksas/adam_intext_pkparam.sas DDMMYYYY HH:MM

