7.5 Noncompartmental Pharmacokinetic Analysis and Parameter Calculation

7.5.1 Plasma Pharmacokinetic Parameters

The appropriate noncompartmental PK parameters will be calculated from the plasma S 48168 (ARM210) concentration-time data using Phoenix® WinNonlin® Version 7.0 or higher sample times will be used in the calculations of the PK parameters. The calculation of the actual time for S 48168 (ARM210) will be in respect to the start of dose administration time of S 48168 (ARM210) on every PK day. All PK parameters included in the protocol are listed in Table 6.1 below, and are defined as appropriate for study design.

Table 6.1. Noncompartmental Pharmacokinetic Parameters to be Calculated (Day 1)

Parameter	Definition	Method of Determination
AUC0-24	Area under the concentration-time curve from time 0 to the 24 hours postdose	Calculated using the Linear Trapezoidal with Linear Interpolation Method. If a value could not be obtained at 24 hours the parameter will be set to missing
AUC0-t	Area under the concentration-time curve from time 0 to the time of the last observed/measured non-zero concentration	Calculated using the Linear Trapezoidal with Linear Interpolation Method
AUC0-inf	Area under the concentration-time curve from time 0 extrapolated to infinity	$AUC0\text{-inf} = AUC0\text{-t} + (Clast/kel)$ where Clast is the last observed/measured concentration
AUC%extrap	Percent of AUC0-inf extrapolated	Calculated as $(1 - AUC0\text{-t}/AUC0\text{-inf}) * 100$
Cmax	The maximum observed concentration	Taken directly from bioanalytical data
Tmax	The time to reach Cmax	Taken from clinical database as the difference in the time of administration and the time of the blood draw which is associated with the Cmax.
Kel	Apparent first-order terminal elimination rate constant calculated from a semi-log plot of the plasma concentration versus time curve.	The parameter will be calculated by linear least-squares regression analysis using the maximum number of points in the terminal log-linear phase (e.g., three or more non-zero plasma concentrations).
t½:	Apparent first-order terminal elimination half-life	Calculated as $0.693/Kel$

Parameter	Definition	Method of Determination
Tlag	Lag time – the time delay between drug administration and the onset of absorption; where onset of absorption	Calculated as the time point prior to the first observed/measured non-zero plasma concentration

Table 6.2. Noncompartmental Pharmacokinetic Parameters to be Calculated (Day 28)

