Parameter	Definition	Method of Determination
AUC0-tau	The area under the concentration versus time curve from the start of drug infusion over the final dosing interval (tau)	Calculated using the linear trapezoidal method with linear interpolation. Tau is equal to 24 hours.
Cmax,ss	The maximum observed concentration at steady state	Taken directly from bioanalytical data
Tmax,ss	The time of the maximum observed concentration at steady state	Taken directly from bioanalytical data. Tmax,ss is the first time point if Cmax,ss occurs at 2 time points
Cmin	Minimum observed concentration at the end of the dosing interval	Taken directly from bioanalytical data
Tmin	Time to reach Cmin	Taken directly from bioanalytical data. Tmin is the first time point if Cmin occurs at 2 time points
RA(AUC)	Accumulation ratio for AUC (steady state versus single dose)	Calculated as AUCtau Day 28/AUC0-24 Day 1
RA(Cmax)	Accumulation ratio for Cmax (steady state versus single dose)	Calculated as Cmax Day 28/Cmax Day 1.
Ctrough_D13	Day 13 Ctrough	Taken directly from bioanalytical data. Day 13 Ctrough is the predose of Day 14

Pharmacokinetic parameters will not be calculated for subjects with less than 2 consecutive postdose time points with quantifiable concentrations. Subjects for whom there are insufficient data to calculate the PK parameters will be included in the concentration tables only and excluded from the descriptive statistics.

Concentrations will be presented in the report at the same precision as received from the bioanalytical laboratory. Concentrations below the lower limit of quantification (LLOQ) will be assigned a value of zero if they occur between time zero (predose) and the first measurable plasma concentration after the first dose and missing thereafter, and will be treated as such for the purpose of calculating PK parameters and summary statistics.

The Kel will be determined using linear regressions composed of least 3 data points. The Kel will not be assigned if 1) the terminal elimination phase is not apparent, 2) if Tmax is one of the 3 last data points, or 3) if the R^2 value is less than 0.8. In cases where the Kel interval is not assigned, the values of $t_{1/2}$, AUC0-inf and AUC%extrap are considered not calculable and will not be reported. Wherever the resulting $t_{1/2}$ is

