- Values for time-based parameters (i.e. Tmax, t1/2) will be presented with 2 decimals. Summary statistics for time-based parameters will be presented as: Mean, Median, and Geom Mean +1; SD +2, Min and Max +0. Accumulation ratios will be presented like time-based parameters.
- Values for rate constants (i.e. Kel) will be presented with 3 significant figures. Summary statistics for Kel will be presented as: Mean, Median, and Geom Mean +1; SD and SEM +2, Min and Max +0.
- CV% and Geom CV% for all parameters will be presented with 1 decimal.
- Remove "Treatment Sequence" and "Study Period" columns from the table.

Program: /CAXXXXX/sas_prg/pksas/pk-tables.sas DDMMMYYYY HH:MM
Program: /CAXXXXX/sas_prg/pksas/adam_pkparam.sas DDMMMYYYY HH:MM

Table 14.2.1.12 will be in the following format.

Page 1 of X

Table 14.2.1.13 Intervals (Hours) Used for Determination of Plasma S 48168 (ARM210) Kel Values
(Pharmacokinetic Population)

Subject Number	Treatment Sequence	Treatment Interval	<X>	R2	n	Treatment Interval	<Y>	R2	n
X	XX	XX.X - XX.X	X.XXX	X	X	XX.X - XX.X	X.XXX	X	X
X	XX	XX.X - XX.X	X.XXX	X	X	XX.X - XX.X	X.XXX	X	X
X	XX	XX.X - XX.X	X.XXX	X	X	XX.X - XX.X	X.XXX	X	X
X	XX	XX.X - XX.X	X.XXX	X	X	XX.X - XX.X	X.XXX	X	X
X	XX	XX.X - XX.X	X.XXX	X	X	XX.X - XX.X	X.XXX	X	X
X	XX	XX.X - XX.X	X.XXX	X	X	XX.X - XX.X	X.XXX	X	X

Treatment <X>: <Label for First Treatment>

Treatment <Y>: <Label for Second Treatment>

R2 = Coefficient of determination

n = Number of points used in Kel calculation

. = Kel value not reportable.

Notes for Generating the Actual Table:

Treatments

- Treatment A: Single oral 120 mg S 48168 (ARM210) QD for 28 days (patients)
- Treatment B: Single oral 200 mg S 48168 (ARM210) QD for 28 days (patients)
- Treatment C: Single oral 120 mg S 48168 (ARM210) QD for 14 days (healthy subjects)
- Treatment D: Single oral 240 mg S 48168 (ARM210) QD for 14 days (healthy subjects)

Presentation of Data:

- Interval start and stop times will be presented to 1 decimal or 3 sig figures min;
- R2 will be presented to 3 decimals;
- n will be presented as an integer (with no decimal)

Programmer Note:

- Use template CPKell for generation of table.

Program: /CAXXXX/sas_prg/pksas/kel-tables-parallel.sas DDMMYYYY HH:MM
Program: /CAXXXX/sas_prg/pksas/adam_kel.sas DDMMYYYY HH:MM

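### Tmin and Tlag are summarised by arithmetic and geometric means although both can be 0, and the SAP gives Cmin, a named endpoint, two incompatible definitions

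*SAP*

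**What the plan says.** **Text tables.** The footnote in SAP 11.1 sets three rules for Tables 11-2 and 11-3: geometric mean and geometric CV% for AUCs and Cmax, median with range for Tmax, and for everything else "Other parameters are presented as arithmetic mean" with SD. The parameter lists in the same section include "Kel <unit>, t½ <unit>, and Tlag <unit>" for Day 1 and "Cmin <unit>, Tmin <unit>, RA(AUC) <unit>" for Day 28, so Tlag and Tmin come under the last rule.

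**Section 14 tables.** SAP 7.6 asks for geometric means and geometric CV%, alongside n, mean, SD, median, minimum and maximum, for the PK parameters with no exclusions. The SAP 11.2 shell carries both geometric rows under every parameter column. Its precision note adds: "Summary statistics for time-based parameters will be presented as: Mean, Median, and Geom Mean +1; SD +2, Min and Max +0".

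**Definitions (SAP 7.5.1).**
- Tlag: "Calculated as the time point prior to the first observed/measured non-zero plasma concentration".
- Cmin: "Minimum observed concentration at the end of the dosing interval".
- Tmin: "Tmin is the first time point if Cmin occurs at 2 time points".

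Protocol 13.1 defines Cmin as the lowest concentration observed and names no time. Cmin is a Day 28 endpoint in protocol 10.2 and SAP 2.2; Tmin and Tlag are secondary PK parameters in SAP 2.2. SAP 9 states that its analyses agree with the protocol's.

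**The concern.** Tmax, Tmin and Tlag are all times read off a sampling grid. The SAP gives Tmax a median with range but not the other two, and offers no reason.

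For **Tlag** the problem is zeros. Anyone quantifiable at the first post-dose sample has a Tlag of 0, and the log of 0 does not exist. The SAP's zero rule covers concentrations below the quantification limit, not derived times.

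For **Tmin** there is a second problem. At steady state the predose and 24 h samples are both troughs. If Cmin is the lowest sample, some people will have their minimum at or near 0 h and others at 24 h, and averaging the two ends describes nobody.

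For **Cmin** the two wordings can give two values of a named endpoint from the same profile. Table 11-3 sets patients beside healthy volunteers, so a definition applied differently to Treatments A and B than to C and D would look like a difference between populations.

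**Working it through.** **1. Inputs from the documents.** Half-life 20 h, median Tmax 3 to 3.5 h and an absorption lag of unstated length (protocol 9.4). Eleven samples per profile including 0.5 h (SAP 7.4), against eight in the amended protocol; its flow chart reads as 0, 1, 2, 4, 6, 8, 12 and 24 h. Three participants dosed so far at each dose level (protocol 11.1).

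**2. Check of the PK model.** The documents give no expected Tmin to reproduce. They do give accumulation ratios of about 1.5-1.8. With daily dosing, 1/(1 − exp(−ln 2 × 24/20)) = 1/(1 − 0.435) = 1.77, which agrees.

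**3. Arithmetic mean of Tmin; no model needed.** Take Tmin of 0, 0.5 and 24 h.
- Mean = 24.5/3 = 8.2 h.
- SD = √[(8.17² + 7.67² + 15.83²)/2] = 13.7 h.
- Median (min, max) = 0.5 (0, 24) h.

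More generally, with k of n people at 24 h and the rest at 0.5 h, the mean is [24k + 0.5(n − k)]/n. For n = 3 the possible values are 0.5, 8.3, 16.2 and 24.0 h. The two middle values are times at which no subject was at minimum.

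**4. Geometric mean.** For the same three values, exp(mean of logs) is undefined, or 0 if the software takes the log of 0 as minus infinity. Computed on the non-zero values alone it is √(0.5 × 24) = 3.5 h. The geometric CV% cannot be computed with the zero included.

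**5. How often a zero occurs.** If each person has probability p of a zero, the chance of at least one in n is 1 − (1 − p)ⁿ. The value of p needs assumptions, so two steady-state one-compartment simulations with a lag were run, both with Cmin as the lowest sample:

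| | Model A | Model B |
|---|---|---|
| Assumed lag | 0.5-1.5 h | 0.25-1.5 h (median) |
| Absorption rate | set to give Tmax 3.25 h | about 1.2/h |
| Assumed noise | CV 3-10% | assay 2-10% plus 5% day-to-day in the trough |
| Expected mean Tmin | about 4.5-12 h (8 samples); 3.2-7.5 h (11 samples) | 2.1-12.1 h (both schedules) |
| At least one Tmin of 0, n = 3 | 41-88% (8 samples) | 50-88% |
| At least one Tmin of 0, n = 8 | 75-100% (8 samples) | 84-100% |

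For example, p = 0.21 gives 1 − 0.79³ = 51%, and p = 0.50 gives 1 − 0.50³ = 88%.

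Under model B, the chance of at least one Tlag of 0 among three people is 1-100% on the SAP schedule and 39-100% on the protocol's, depending almost entirely on the assumed lag. Zeros are likelier on the protocol schedule because its first post-dose sample is at 1 h rather than 0.5 h.

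**6. The two readings of Cmin.** If Cmin is the end-of-interval value, it is the 24 h sample and Tmin is about 24 h for everyone. A rule for Cmin occurring at two time points then has nothing to do; it makes sense only if Cmin is the lowest of all samples, as in protocol 13.1. Under model A the ratio of the average lowest sample to the average 24 h value was 0.905-0.983, a difference of about 2-10%.

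**The case against.** - **Little depends on it.** PK is exploratory, SAP 7.7 rules out formal testing, and Tmin and Tlag are secondary parameters. The Section 14 tables, the source for the text tables, list every subject and print median, minimum and maximum. This stands: no data are lost, and the fault is in what the text table shows.
- **Undefined values are catered for.** The shells allow a missing or not-reportable entry, and nothing in the documents shows that zeros would be silently dropped. This stands in part: the outcome is unspecified rather than known to be wrong.
- **The shells may change.** SAP 11 allows this for unforeseen circumstances. Zeros are foreseeable, and SAP 7.6 is body text.
- **The time-parameter note in SAP 11.2 names only Tmax and half-life and concerns decimals.** Correct; the wider requirement comes from SAP 7.6 and the shell rows.
- **A median can be less stable.** When 0, 0, 24 h becomes 0, 24, 24 h, the mean moves from 8 to 16 h but the median jumps from 0 to 24 h. This stands, and is why the fix adds counts.

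A reader might go further and infer that the mean Tmin will land at about 3-12 h, near the concentration peak. The documents do not support this. They give no lag length, noise level or expected Tmin. Under model B a single group's mean fell in that window in only 14-46% of groups of three and 36-80% of groups of eight. Only the low end is near the stated Tmax, and on the literal SAP wording of Cmin the mean is about 24 h.

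A reader might also infer that Cmin and the accumulation ratios must move to the geometric scale in the text tables. That is a preference: at the protocol's CV of about 15%, the arithmetic mean exceeds the geometric by √(1 + 0.15²) − 1 = 1%, and Section 14 prints both.

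**Conclusion.** The point holds as a minor reporting defect. Three parts rest on the text alone: Tmin and Tlag are assigned mean ± SD; geometric statistics are required for parameters that can be 0; and the SAP's Cmin wording conflicts with its own tie rule and with the protocol. The Cmin conflict matters most, because Cmin is a named endpoint.

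The averaging problem for Tmin, and its zeros, arise only if Cmin is the lowest sample; Tlag zeros arise on either reading. How often zeros occur, where the mean Tmin falls, and the 2-10% gap between the Cmin readings all depend on the assumed lag and noise. A reader might take a shifted Tmin row in Table 11-3 as a disease effect, but n and SD are in the same cell and no decision in the plan uses Tmin.

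**What to change.** 1. **SAP 11.1 footnote:** add Tmin and Tlag to the median (min, max) rule. For Tmin also give the number of subjects at each nominal time, because the median can sit at one end when the split is about even.
2. **SAP 7.6 and 11.2:** omit the geometric mean and geometric CV% for Tmax, Tmin and Tlag.
3. **SAP Table 6.2:** define Cmin as the lowest observed concentration in the steady-state profile, as in protocol 13.1, and apply this to Treatments A-D (Day 28 in patients, Day 14 in healthy subjects). If the 24 h value is wanted, report it separately under its own name.

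The cost is a few lines of SAP text and a table-program setting. No new data are needed, and the median, minimum and maximum are already calculated. The scale for Cmin and the accumulation ratios can stay as it is.
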